5.2.4.1 ASSESSMENT OF ALLERGIC SYMPTOMS

In brief, symptoms will be monitored during the challenge, with detailed assessment prior to each challenge dose, according to Figure 3.

- **Green** symptoms: Not generally sufficient to consider a challenge positive.
- **Orange** symptoms: Symptoms that recur on 3 doses, or persist (e.g. 40 minutes) are more likely indicative of a reaction than when such symptoms are transient and not reproducible. - 3 or more scoring areas in orange, more likely represent a true response.
- **Red** symptoms: A single red symptom is likely to indicate a true response, and if present the challenge should be halted.

The outcome of the challenge (positive or negative) and the apparent eliciting threshold dose will be recorded in the participant record. Challenge outcome will be determined as per the PRACTALL Consensus criteria,⁹ as shown in Figure 3; where possible, challenges should be stopped on the basis of at least one objective symptom:

¹² Howie SRC. Blood sample volumes in child health research: review of safe limits. Bulletin of the World Health Organization 2011;89:46-53. doi: 10.2471/BLT.10.080010

I. SKIN
A. Pruritus
0 = Absent
1 = Occasional scratching
2 = Scratching continuously for >2 minutes at a time
3 = Hard continuous scratching causing excoriations
B. Urticaria/Angioedema
0 = Absent
1 = < 3 hives, or mild lip oedema
2 = < 10 hives but >3, or significant lip, tongue or facial oedema
3 = Generalized involvement
C. Rash
0 = Absent
1 = Few areas of faint erythema
2 = Areas of erythema
3 = Generalized marked erythema (>50%)
II. UPPER RESPIRATORY
A. Sneezing/Itching
0 = Absent
1 = Rare bursts, occasional sniffing
2 = Bursts <10, intermittent rubbing of nose/eyes or frequent sniffing
3 = Continuous nasal/eye itch, periocular swelling and/or long bursts of sneezing, persistent rhinorrhoea
III. LOWER RESPIRATORY
A. Wheezing
0 = Absent
1 = Expiratory wheeze on auscultation
2 = Biphasic wheeze
3 = Use of accessory muscles, audible wheezing
B. Laryngeal
0 = Absent
1 = >3 discrete episodes of throat clearing/cough, or persistent throat tightness/pain
2 = Vocal hoarseness, frequent cough
3 = Stridor
IV. GASTROINTESTINAL
A. Subjective Complaints
0 = Absent
1 = Complaints of nausea or abdominal pain, itchy mouth/throat
2 = Frequent c/o nausea or pain with normal activity
3 = Notably distressed due to GI symptoms with decreased activity
B. Objective Complaints
0 = Absent
1 = 1 episode of emesis
2 = 2-3 episodes of emesis or diarrhoea or 1 of each
3 = >3 episodes of emesis or diarrhoea or 2 of each
V. CARDIOVASCULAR/NEUROLOGIC
0 = normal heart rate or BP for age/baseline
1 = Subjective symptoms (weak, dizzy), or tachycardia
2 = Drop in mean BP of >20% from baseline, or significant change in mental status.
3 = Cardiovascular collapse, signs of impaired circulation (unconscious)

Figure 3: PRACTALL consensus stopping criteria for food challenges.⁹

5.2.5 MANAGEMENT OF SYMPTOMS DURING DBPCFC IN HOSPITAL

Any allergic reaction occurring during in-hospital food challenge will be managed according to established local protocol and consistent with national guidelines. The UK Resuscitation Council guideline is shown below for information only. A suggested protocol for the management of refractory anaphylaxis appears in Appendix 1.

[figure not shown]

Figure 4: UK Resuscitation Council guideline for management of Anaphylaxis

5.3 TREATMENT ALLOCATION AND PHASE 1 INTERVENTION

Eligible participants (who have a positive DBPCFC, confirming IgE-mediated CM allergy) will be allocated using minimisation to one of three interventional arms, either:

- GROUP S (Sublingual): SLIT.
- GROUP O: Low dose OIT (CM protein taken orally, at the same doses used in Group S).
- GROUP C: Placebo Control. Participants in group C will be randomized (1:1) to either placebo SLIT or placebo OIT.

5.3.1 TREATMENT ALLOCATION

[figure not shown]
OIT outcomes are affected by a range of variables, including age, allergen-specific IgE to CM, threshold and the presence of asthma. It is therefore essential to maintain balance between treatment groups with respect to these predictors. However, stratified randomisation using several variables is not effective in small trials. Minimisation is a valid alternative to ordinary randomisation, and has the advantage that there will be only minor differences between groups in baseline variables which are used in the allocation process.¹³ With minimisation, the treatment allocated to the next participant enrolled in the trial depends on the characteristics of those participants already enrolled, with an element of weighted randomisation – typically 80% chance – of each participant getting the allocation that minimises any imbalance.

Participants will therefore be allocated using an online minimisation/randomization tool, Minim, with a random element using a weighting probability of 0.8, stratified by centre. Baseline variables included in the minimisation will be:

- age (under 12yrs, 13+yrs)
- sex
- specific IgE to CM (<30 kU/l, \geq 30 kU/l)³
- eliciting dose at DBPCFC (\leq 44mg, 144-444mg, $>$ 444mg CM protein; these cut-offs are based on published population-based dose distributions in CM-allergic children)
- documented tolerance to CM in baked foods (tolerant or allergic/unknown).
- asthma (none, no regular inhaled corticosteroid (equivalent to BST Step 1), regular ICS (equivalent to BTS Step 2 or above).

Group allocation (active vs placebo) will be concealed throughout the study until completion of the 2nd visit of the exit DBPCFC at 12 months.

The schema for treatment allocation will be as follows:

¹³ Altman DG, Bland JM. Treatment allocation by minimisation. BMJ. 2005 Apr 9; 330(7495): 843.

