6. **Post phase 2 assessment:** All subjects will undergo an exit DBPCFC to CM to determine any change in threshold to CM. Blinding as to the phase 1 intervention will be preserved until after completion.

All participants will be advised on current best practice for CM allergy, i.e. CM avoidance (except for study doses) plus provision of rescue medication and training) for the duration of the study.

The impact of CM immunotherapy on HRQL will be assessed prior to, and after each phase in all subjects (and their parents), using validated questionnaires, with the final assessment 3 months after completing Phase 2.

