3.1.2. SECONDARY STUDY OUTCOMES

- Proportion of participants experiencing adverse events classified as mild non-transient symptoms or more severe (see table 9) during CM-OIT (phase 2), in those who have received SLIT pretreatment (group S) compared to the equivalent SLIT dose orally during phase 1 (group O).
- Other safety outcomes in the different treatment groups (withdrawals due to intervention, anaphylaxis rate/adrenaline use)
- Efficacy defined at DBPCFC as the proportion of study participants experiencing:
 - i. No symptoms (or only mild transient symptoms as per table 9) to 8 grams CM protein (approx. 250mls fresh milk) ("Complete desensitisation")
 - ii. No symptoms (or only mild transient symptoms as per table 9) to at least 1.4 grams CM protein (approx. 45mls fresh milk) ("Partial desensitisation")
 - iii. At least a 10-fold increase in eliciting dose (defined as the lowest dose which elicits objective symptoms or signs at challenge).

Efficacy at 6 and 12 months will be compared across all treatment groups (including SLIT pretreatment) vs the equivalent dose administered orally without a sublingual phase (to address hypothesis 2).

- Immunological outcomes (titrated skin prick test, serum IgE) at baseline, 6 and 12 months.
- Change in health-related quality of life (HRQL) measures at 6, 12 and 15 months, as assessed by validated questionnaires (FAQLQ, FAIM, EQ-5D, self-efficacy) in study participants and their parents.

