5.7 HRQL ASSESSMENT AT 15 MONTHS

HRQL will also be assessed 3 months after the exit DBPCFC. This can be done by email/online if preferred by the participant and their family.

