5.8.2 QUALITY OF LIFE ASSESSMENTS

The impact of OIT on participants' health-related quality of life (HRQL) will be assessed both from parents' and participants' perspective using abbreviated versions of disease-specific validated "food-allergy quality of life questionnaire" (FAQL-Q) in its parental,¹⁵ child¹⁶ and teenage¹⁷ forms at five time points during the study:

- i. baseline, at screening
- ii. baseline, after completion of the baseline DBPCFC
- iii. prior to the DBPCFC in between Phase 1 and Phase 2, at around 6 months
- iv. prior to the exit DBPCFC after Phase 2.
- v. 3 months after the exit DBPCFC (15 months visit).

These new abbreviated versions have been validated (data submitted for publication). We will also assess the impact of the child's food allergy on parent QoL using the FAQL-Parent Burden form (which has been validated in a UK population).¹⁸

The FAQL-questionnaires are based on a 7-point Likert scale and changes greater than 0.5 points over time have been defined as clinically significant.¹⁹ Previous studies have reported a positive effect on QoL following OIT to CM from the parents' perspective.²⁰ However, there are no controlled studies which have addressed the impact on QoL as perceived by the participants themselves. This is a significant knowledge gap, since there is a concern that while parents report an improved HRQL when their child undergoes immunotherapy the child themselves may experience a worsening of HRQL measures due to frequent side effects and need to alter their activities following immunotherapy doses.

In line with current expert opinion, and to ensure the ability to compare responses consistently during the 12 months of OIT, children who are age 12 at study commencement will be asked to complete the Teenage versions of the QoL assessments unless there are difficulties with comprehension which preclude this.

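### Concealment of the Phase 1 arm may end at the 12-month exit challenge, about three months before the self-reported 15-month quality-of-life outcome

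*Combined protocol and SAP*

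**What the plan says.** Section 5.3.1 states that group allocation, meaning active versus placebo, "will be concealed throughout the study until completion of the 2nd visit of the exit DBPCFC at 12 months". The summary of study components in section 3 makes a looser statement under item 6, the post-Phase 2 assessment: "Blinding as to the phase 1 intervention will be preserved until after completion". It does not say completion of what.

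The secondary outcomes in section 3.1.2 include "Change in health-related quality of life (HRQL) measures at 6, 12 and 15 months, as assessed by validated questionnaires", and section 7.2.2 lists the same time points for analysis. Section 5.8.2 has both the child and the parents answering. It places the 12-month questionnaire "prior to the exit DBPCFC after Phase 2". Section 5.7 adds: "HRQL will also be assessed 3 months after the exit DBPCFC", with email or online completion allowed. Section 5.9 gives a study duration of about 15 months per participant.

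Section 5.3.2.2 provides for an unblinded team member who prepares the Phase 1 doses and does not assess outcomes.

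**The concern.** The trigger that ends concealment is a visit by one participant, and nothing defers it until that participant's last outcome. The last outcome is a subjective questionnaire. A child or parent who has learned that Phase 1 was active, or was placebo, may answer differently for that reason alone. A difference between arms at 15 months could then reflect knowledge of the arm as well as any lasting effect of the pretreatment.

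The protocol gives reasons to care about this. Section 3.2 justifies the placebo arm partly because reactions to placebo are common in food immunotherapy. Section 5.8.2 presents the child's own view of quality of life as a gap left by the lack of controlled studies. No section says how the 15-month analysis would allow for respondents who know their arm.

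**Working it through.** No sample-size or power figure bears on this point. The check is a comparison of timelines.

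**1. Order of events for one participant**

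| Event | Timing | Source | Relative to end of concealment |
|---|---|---|---|
| HRQL after Phase 1 | about month 6, before the interim challenge | 5.8.2 | before |
| Adverse events in Phase 2 (primary outcome) | the 6 months of Phase 2 | 3.1.1, 5.5 | before |
| HRQL after Phase 2 | about month 12, before the exit challenge | 5.8.2 | before |
| Exit challenge, second visit | about month 12 | 5.3.1, 5.6.1 | concealment ends on completion |
| Final HRQL | 12 + 3 = 15 months | 5.7, 5.8.2 | after, by 15 − 12 = about 3 months |

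Of the three post-baseline HRQL time points (6, 12 and 15 months), one falls after concealment ends.

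**2. Does section 3 close the gap?** If completion in item 6 means completion of the exit challenge, under which it sits, it agrees with section 5.3.1 and the gap stays. If it means completion of the study, it conflicts with section 5.3.1, because section 5.9 puts the end at about 15 months and section 5.3.1 stops at 12. Section 5.3.1 is the more specific text. On either reading the two places need to be aligned.

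**3. What would be newly learned?** The route, sublingual or swallowed, is already known to the family from the dosing instructions in section 5.3.2. Only active versus placebo is masked, so the exposure falls mainly on comparisons of groups S and O with group C.

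**4. How many could be affected?** With 22 per arm and the 10% loss assumed in section 7.1, 22 × 0.90 = 19.8, or about 20 per arm. That is an upper bound, reached only if every completer is told before answering.

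**5. When could arms first become known at a site?** Phase 1 lasts 4 to 7 months and Phase 2 lasts 6 (section 3). The earliest reveal is therefore 4 + 6 = 10 to 7 + 6 = 13 months after a participant starts treatment. The recruitment span is not stated.

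**The case against.** The strongest reply is that little is at stake. By month 15 every family has had 6 months of open-label oral immunotherapy and dietary advice tied to the exit result (sections 5.5 and 5.6.2). Some may already suspect their arm from the interim challenge and the Phase 2 starting step. The HRQL objective in section 2.2 concerns milk immunotherapy in general, and neither section 3.1.2 nor section 7.2.2 names an HRQL contrast between S and C. For change within participants, knowing the Phase 1 arm matters much less. All of this stands and keeps the point small. It does not remove it: section 7.2.2 lists 15-month HRQL for testing in a three-arm trial, and a comparison by arm is a natural use of those data.

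A reader might also infer more than the documents support:

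- **That every child is told the arm at 12 months.** Section 5.3.1 says when concealment ends. It describes no disclosure step and does not say who is told. Participant-by-participant release is the natural reading, but it remains an inference.
- **That later allocations become readily predictable.** Minimisation runs "with a random element using a weighting probability of 0.8, stratified by centre", so known earlier arms carry some information about the next one. However, reveals lag the start of treatment by about 10 to 13 months, so the most recent arms always stay hidden and a site could not reconstruct the full imbalance this way. If recruitment ends before the first exit challenges, nothing leaks. At most, longer recruitment could make later allocations somewhat more predictable.
- **That no care decision needs the arm.** Section 5.6.2 bases advice on the exit threshold and, for those tolerating at least 1.4 g, the dose already being taken. For children reacting below 1.4 g it defers to local clinical protocol, which is not in the documents.

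**Conclusion.** The point holds in a narrow form. As written, section 5.3.1 lets concealment of active versus placebo end about three months before a listed secondary outcome that families report themselves, and no other section covers the interval. One of three post-baseline HRQL time points may therefore be collected with the arm known. The primary outcome, the exit challenge and HRQL at 6 and 12 months are unaffected.

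The conclusion assumes that concealment ends participant by participant and that some families learn their arm before answering. It bears on comparisons between arms at 15 months. The documents hold no figure from which an expectation effect could be derived. The 0.5-point threshold in section 5.8.2 defines a clinically significant change over time and says nothing about the size of a bias.

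**What to change.** Amend section 5.3.1 so that allocation stays concealed from the participant, the family and blinded study staff at least until that participant's 15-month HRQL assessment is complete, apart from emergency unblinding. The unblinded dose preparer in section 5.3.2.2 is outside this rule. Reword item 6 in section 3 to name the same point and to say who is told. State also what applies to a child withdrawn early, who may never reach the exit challenge and whose HRQL is due three months after withdrawal (section 4.3).

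If disclosure at 12 months is intended, keep it, but say so, and label any comparison of 15-month HRQL between arms as unblinded in section 7.2.2.

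Holding concealment until the last participant finishes or the database is locked would go further than the HRQL problem requires.

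The cost is a short text change in two places and a wait of about three more months before families learn their Phase 1 arm. No visit, sample or assessment changes.

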5.3.2. PHASE 1 (PRETREATMENT)

Following allocation, patients will commence phase 1 (pretreatment), as follows:

- Group S: Participants will receive daily SLIT for approximately 4-7 months using concentrated powdered milk with a top dose of 60mg of CM protein. Participants will be instructed to keep the SLIT dose under the tongue for 2 minutes and then swallowed ("sublingual route").
- Group O: Participants receive OIT for approximately 4-7 months using the same product and dosing protocol as that used in Group S. However, the daily dose will be administered straight into the mouth and immediately swallowed and the mouth rinsed afterwards ("oral route").
- Group C: Participants receive placebo. Participants in this group will be randomized (1:1) to either placebo SLIT or placebo OIT, following the same instructions as above.

Participants will receive daily doses of CM or placebo at home. Dose increases will be performed under medical supervision on the Research Unit, according to the updosing regime in Table 4.

5.3.2.1. INITIAL ESCALATION DAY

Phase 1 will start with an "escalation day" visit in which up to 7 consecutive doses (starting with 0.01 mg of CM protein) will be given, every 30-60 minutes (Table 4) under medical supervision. Doses will be given either by the sublingual or the oral route according to group allocation.

Participant will be assessed prior to dosing to ensure suitability, as described in section 5.2.1. If a given dose triggers symptoms which cause discomfort to the participant (such as sustained oral itch) or deemed to be significant by the research team, no further doses will be administered on the escalation day.

Participants and/or their family will then be instructed to take the last well-tolerated dose on a daily basis at home, for a minimum of 10 days until the next increase is performed.

PHASE 1 UPDOSING PROTOCOL

Steps	CM protein (mg)	Volume of mix (ml)
Step 1	0.01	0.5
Step 2	0.02	0.5
Step 3	0.04	0.5
Step 4	0.08	0.5
Step 5	0.2	0.5
Step 6	0.4	0.5
Step 7	1	0.5
Step 8	2.5	0.5
Step 9	6	0.5
Step 10	15	0.5
Step 11	30	0.5
Step 12	60	0.5

Table 4: Updosing protocol for phase 1 CM immunotherapy pretreatment

Each step will be administered daily at home for a minimum of 10 days. Once the target dose is achieved (step 12), participants will continue this dose on a daily basis for a target of 16 weeks. The duration of Phase 1 will vary from participant to participant, with the aim of achieving Step 12 within 12 weeks and maintaining Step 12 for 16 weeks. Thus, the duration of Phase will vary from approximately 4 to 7 months, at which time the DBPCFC assessment will be completed and phase 2 intervention commenced.

The starting point in phase 1 (initial dose to be administered on the escalation day) will be individualised based on the outcome of the screening DBPCFC, as shown in Table 5. The NOAEL (No Observed Adverse Event Level or highest dose *not* triggering symptoms) will be used for this purpose, defined as the lowest dose tolerated at DBPCFC excluding transient Grade 1 symptoms (see Table 9).

Tolerated dose (NOAEL) at baseline DBPCFC	Initial dose for Phase 1		Max dose at Initial Escalation day		Max number of doses at initial escalation
	Step	CM Protein (mg)	Step	CM Protein (mg)	
<0.5mg (i.e. symptoms at first dose during DBPCFC)	1	0.01	7	1	7
0.5mg	5	0.2	8	2.5	4
3mg	6	0.4	9	6	4
10mg	8	2.5	10	15	3
30mg	9	6	11	30	3
100mg	10	15	12	60	3
300mg	11	30	12	60	2

Table 5. Starting dose for OIT in Phase 1.

Prior to discharge home, each family will be provided with:

- A **symptom advice sheet** (including advice on avoiding intense physical exercise up to 2 hours after the dose intake).
- A **food allergy management plan** (example in Figure 4), including an emergency medicine kit containing non-sedating oral antihistamine, two adrenaline auto-injector devices and a salbutamol inhaler with spacer device. Families and participants will be instructed in the prompt recognition and treatment of allergic reactions, including adrenaline auto-injectors. The expiry date of auto-injection devices will be checked, and a prescription for replacements provided if needed.
- **Contact information** for the team, which will include a dedicated mobile phone number with 24/7 access to a member of the medical team for urgent queries, and an email address which will be checked daily by the research team from Monday to Friday for non-urgent queries.
- **Dietary advice on CM avoidance.** Participants will be given instructions to avoid all CM or CM-containing foods during the study, with the exception of study immunotherapy doses. Up to 70% of children with CM allergy tolerate the allergen when extensively heated, such as in a cake or biscuit: the heating, in a wheat-containing matrix, significantly modifies CM allergenicity. Participants who are able to tolerate baked foods containing CM, will be requested to avoid all CM including in baked foods during the study, since uncontrolled exposure to CM protein in baked foods will impact upon treatment outcomes.
- A **home diary and instruction sheet**, which will specify to participants/parents what study dose to give their child, and on to which they will log all doses taken at home and any resulting adverse events. Subjects will be asked to record any symptoms, duration, timing in relation to immunotherapy dose and any exacerbating factors (e.g. exercise, excessive tiredness, viral illness). In the event of any symptoms, the family needs to contact the research team for advice.

At subsequent increases, the dose will first be given (by either the sublingual or oral route, depending on allocation) under medical supervision, followed by observation for at least one hour (2 hours if participant has previously experienced a delayed reaction). Prior to updosing, the supervising clinician will assess the participant to ensure:

- No significant allergic reactions to doses given in previous 2 weeks.
- No acute exacerbation of asthma in the past week.
- No concurrent systemic illness.

ALLERGY ACTION PLAN

bsaci
improving allergy care
through education, training and research

RCPCH Anaphylaxis
Royal College of
Paediatrics and Child Health
Leading the way in Children's Health
Allergy UK

This child has the following allergies:

Name: _____

DOB: _____

Photo

Mild/moderate reaction:

- Swollen lips, face or eyes
- Itchy/tingling mouth
- Hives or itchy skin rash
- Abdominal pain or vomiting
- Sudden change in behaviour

Action to take:

- Stay with the child, call for help if necessary
- Locate adrenaline autoinjector(s)
- Give antihistamine:

(If vomited,
can repeat dose)

- Phone parent/emergency contact

Emergency contact details:

1) Name: _____

2) Name: _____

Parental consent: I hereby authorise school staff to administer the medicines listed on this plan, including a 'spare' back-up adrenaline autoinjector (AAI) if available, in accordance with Department of Health Guidance on the use of AAI in schools.

Signed: _____

Print name: _____

Date: _____

For more information about managing anaphylaxis in schools and "spare" back-up adrenaline autoinjectors, visit:
sparepensinschools.uk

© The British Society for Allergy & Clinical Immunology 6/2018

Watch for signs of ANAPHYLAXIS

(life-threatening allergic reaction)

Anaphylaxis may occur without skin symptoms: ALWAYS consider anaphylaxis in someone with known food allergy who has **SUDDEN BREATHING DIFFICULTY**

A AIRWAY

- Persistent cough
- Hoarse voice
- Difficulty swallowing
- Swollen tongue

B BREATHING

- Difficult or noisy breathing
- Wheeze or persistent cough

C CONSCIOUSNESS

- Persistent dizziness
- Pale or floppy
- Suddenly sleepy
- Collapse/unconscious

IF ANY ONE (OR MORE) OF THESE SIGNS ABOVE ARE PRESENT:

1 Lie child flat with legs raised (if breathing is difficult, allow child to sit)

2 Use Adrenaline autoinjector **without delay** (eg. EpiPen®) (Dose: mg)

3 Dial 999 for ambulance and say ANAPHYLAXIS ("ANA-FIL-AX-IS")

[figure not shown]

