5.2.1 CLINICAL ASSESSMENT AND CHECKS PRIOR TO DBPCFC

All subjects will be assessed prior to DBPCFC to determine suitability for a challenge, as follows:

- No intercurrent illness (viral or otherwise)
- No exacerbation in allergic symptoms (eczema, asthma, food allergy) in the preceding week.
- No short-acting β 2 agonists used in the past 12 hours
- No recent antihistamine exposure (e.g. cetirizine, loratadine) in the past 48 hours (72 hours for fexofenadine, 5 days for long-acting antihistamine (e.g. chlorphenamine, desloratadine).
- No oral steroids have been taken in the past 2 weeks
- Baseline observations (temperature, blood pressure, heart and respiratory rate, oxygen saturations, PEFR) within the normal range.
- Baseline physical examination must not reveal any significant acute findings.

Challenges will occur on a Challenge Unit with staff fully trained in the management of allergic reactions including anaphylaxis. Emergency equipment (including oxygen and suction) and medication will be checked beforehand, as per local protocol and international criteria for performance of DBPCFC.

5.2.2 DBPCFC AT BASELINE AND FOLLOWING PHASE 1

The challenge will consist of up to eight incremental doses of CM/placebo given at 20-30 minute intervals, followed by an observation period of 2 hours, as shown in table 2.

Published data indicates that the eliciting dose in milk-allergic patients may be lower than for other food allergens. As a safety measure, during the baseline DBPCFC, the dosing interval between the first (0.5mg) and second (3mg) doses will be extended to 60 minutes. The additional 30 minutes will allow for the detection of symptoms in the most sensitive participants, thus limiting the chance of further but unnecessary CM doses being given.

¹¹Sampson HA, Gerth van Wijk R, Bindslev-Jensen C, et al. Standardizing double-blind, placebo-controlled oral food challenges: AAAAI-EAACI PRACTALL consensus report. J Allergy Clin Immunol. 2012;130:1260-74.

The time intervals following other doses may be extended up to one hour at the local investigator's discretion, where the participant may be experiencing an evolving reaction (as a safety measure, to limit the dose which might in turn moderate the symptoms experienced at challenge).

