5.5.1 INITIAL UPDOSING / DOSE ESCALATION DAY

The starting dose of OIT in phase 2 will be individualised based on the outcome of the interim DBPCFC at 4-7 months, as shown in Table 7. The NOAEL (No Observed Adverse Event Level or highest dose not triggering symptoms) will be used as the tolerated dose. Mild transient symptoms (e.g. itchy mouth) to the reference dose (transient COFAR Grade 1 symptoms (Table 9) might be acceptable.

Tolerated dose (NOAEL) at 6 months DBPCFC	Initial dose for Phase 2 OIT		Max dose at Initial Escalation day	
	Step	CM Protein (mg)	Step	CM Protein (mg)
<0.5mg (i.e. 1 st dose reactor at FC)	1	0.04	6	2.5
0.5mg	3	0.2	6	2.5
3mg	4	0.4	7	6
10mg	6	2.5	8	15
30mg	9	30	n/a	n/a
100mg	10	60	n/a	n/a
300mg	10	60	n/a	n/a
1000mg or more	11	135	n/a	n/a

Table 7. Starting dose for OIT in Phase 2.

Participants starting phase 2 OIT at steps 1-6 will be offered to attend an escalation day visit at which up to 6 consecutive doses will be given by mouth at 20-30 minutes intervals under medical supervision on the Research Unit. As described in 5.3.2.1 (phase 1 escalation day), the supervising clinician will assess the participant to ensure suitability prior to dosing. If a given dose triggers symptoms that cause discomfort to the participant or deemed significant by the research team, no further doses will be administered on that day. Participants will be observed for at least one hour after dosing (2 hours if participant has previously experienced a delayed reaction). Participants will be instructed to have the last well-tolerated dose at home on a daily basis for a minimum of 10 days, until the next increase is performed.

At the discretion of the local investigator, participants commencing phase 2 OIT at step 9 or above do not need to attend for a separate escalation day:

- If the 2nd DBPCFC visit (at 6 months) is ACTIVE, then they can start the OIT dose the next day at home, unless there is doubt as to the dose tolerated at challenge (in which case a separate initiation visit should take place).
- If the 2nd DBPCFC visit is PLACEBO, then the initial OIT dose(s) can be given at the end of the 2 hour observation period of the challenge, where time permits.

Participants will then be asked to have their daily dose at home for a minimum of 10 days until the next increase is performed.

Prior to discharge home, patients will receive instructions including symptoms management and reporting as described in **5.3.2.1**.

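### Section 5.3.2.1 defines the NOAEL that sets the Phase 1 starting step in two incompatible ways in one sentence, and the handling of transient Grade 1 symptoms is not settled across the two phases

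*Combined protocol and SAP*

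**What the plan says.** Section 5.3.2.1 says the Phase 1 starting point "will be individualised based on the outcome of the screening DBPCFC, as shown in Table 5". Table 5 is entered through its first column, headed "Tolerated dose (NOAEL) at baseline DBPCFC". Its lowest row is "<0.5mg (i.e. symptoms at first dose during DBPCFC"), followed by rows for 0.5, 3, 10, 30, 100 and 300 mg.

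The sentence that defines the NOAEL opens with "The NOAEL (No Observed Adverse Event Level or highest dose *not* triggering symptoms) will be used for this purpose" and continues "defined as the lowest dose tolerated at DBPCFC excluding transient Grade 1 symptoms".

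For Phase 2, section 5.5.1 gives only one of these wordings: "The NOAEL (No Observed Adverse Event Level or highest dose not triggering symptoms) will be used as the tolerated dose". It adds that mild transient symptoms at the reference dose may be allowed, without saying when or by whose decision.

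**The concern.** The words after the gloss are presented as the definition, and they say the opposite of the gloss. In a challenge that climbs from 0.5 mg, the lowest tolerated dose and the highest dose without symptoms are different quantities for any child who tolerates more than one dose. The NOAEL fixes the Phase 1 starting step, the ceiling on the escalation day and hence the shortest time to maintenance. Staff who follow the defining words and staff who follow the gloss would enter different rows of Table 5.

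A smaller mismatch concerns transient Grade 1 symptoms. The gloss in section 5.3.2.1 allows no symptoms, the definition after it disregards transient Grade 1 symptoms, and section 5.5.1 leaves the matter open. In Phase 2 this can decide the starting row and whether the child is offered an escalation day.

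**Working it through.** The plan gives no figure to reproduce, so the check maps each possible baseline result to Table 5 under both wordings.

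**Inputs**
- Challenge doses (section 5.2.2, Table 2): 0.5, 3, 10, 30, 100, 300, 1000 and 3000 mg, ascending.
- Eligibility (section 4.1): reaction at 1.44 g or less. The cumulative dose through the 1000 mg step is 0.5 + 3 + 10 + 30 + 100 + 300 + 1000 = 1443.5 mg, so 1000 mg is taken as the last eligible first-reaction dose. This matches Table 5, which ends at a NOAEL of 300 mg.
- Starting doses and escalation-day ceilings: Table 5. Its counts are internally consistent: ceiling step − starting step + 1 equals the stated maximum number of doses in all seven rows (7, 4, 4, 3, 3, 3, 2).
- At least 10 days per step, then a target of 16 weeks at step 12 (section 5.3.2.1).

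Assumption: each child tolerates every dose below the first reaction.

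**Step 1: starting dose.** Ratio = Table 5 starting dose under the highest-dose wording ÷ that under the lowest-dose wording.

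| First reaction (mg) | Highest-dose wording: row → start (mg) | Lowest-dose wording: row → start (mg) | Ratio |
|---|---|---|---|
| 0.5 | <0.5 → 0.01 | <0.5 → 0.01 | 1 |
| 3 | 0.5 → 0.2 | 0.5 → 0.2 | 1 |
| 10 | 3 → 0.4 | 0.5 → 0.2 | 2 |
| 30 | 10 → 2.5 | 0.5 → 0.2 | 12.5 |
| 100 | 30 → 6 | 0.5 → 0.2 | 30 |
| 300 | 100 → 15 | 0.5 → 0.2 | 75 |
| 1000 | 300 → 30 | 0.5 → 0.2 | 150 |

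Under the lowest-dose wording, the 3, 10, 30, 100 and 300 mg rows (five of seven) can never be reached.

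**Step 2: shortest Phase 1.** Minimum build-up = (12 − ceiling step) × 10 days. Minimum Phase 1 = build-up + 16 × 7 = build-up + 112 days.
- Row <0.5 mg (ceiling step 7): 50 + 112 = 162 days.
- Row 0.5 mg (ceiling step 8): 40 + 112 = 152 days.
- Rows 100 and 300 mg (ceiling step 12): 0 + 112 = 112 days.

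At 365/12 = 30.4 days per month, 112 days is 3.7 months and 152 days is 5.0 months. Under the lowest-dose wording no child could finish in under about 5.0 months if the 16-week target is kept. Under the other wording the shortest course is 3.7 months, which fits the lower end of the stated 4 to 7 months.

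**Step 3: transient symptoms.** Take a child with brief oral itch at 30 mg and a clear reaction at 100 mg.

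| Itch | NOAEL | Table 5 start | Table 7 start |
|---|---|---|---|
| Counted | 10 mg | step 8, 2.5 mg | step 6, 2.5 mg, escalation day offered |
| Disregarded | 30 mg | step 9, 6 mg | step 9, 30 mg, escalation day not applicable |

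The ratio is 6 / 2.5 = 2.4 in Table 5 and 30 / 2.5 = 12 in Table 7. Section 5.5.1 also lets children starting at step 9 or above, at the local investigator's discretion, take the first dose at home the day after an active second challenge visit, unless the tolerated dose is in doubt. How the itch is counted can therefore affect whether the first Phase 2 dose is supervised.

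**The case against.** The strongest reply is that nobody could run the trial on the lowest-dose wording. It would empty most of Table 5, remove nearly all of the individualisation that section 5.3.2.1 announces, conflict with the stated Phase 1 duration and depart from section 5.5.1. Staff using Table 5 would probably notice. This stands as a reason to expect a slip rather than two working rules. It does not cure the text, because the conflicting words are the ones offered as the definition and nothing elsewhere corrects them.

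Several stronger inferences are tempting but not supported:
- **Unsafe first doses.** The lowest-dose wording gives an equal or lower starting dose in every row of the comparison, and the escalation day is supervised.
- **A different pretreatment.** The maintenance target is step 12 for 16 weeks under either wording, and the 40-day minimum build-up from the 0.5 mg row lies within the 12-week aim (84 days).
- **Bias in the primary comparison.** Allocation is stratified by centre and minimised on eliciting dose (section 5.3.1), Phase 1 is double-blind, and allocation stays concealed until the exit challenge. A reading adopted by one site would apply to all its arms.
- **One challenge giving two NOAELs.** Phase 1 uses the baseline challenge and Phase 2 the interim one, so this does not arise.
- **150-fold as the typical size.** It is the extreme of a range that starts at no difference.

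On transient symptoms, it is fair to say that the Phase 1 definition can be read as refining its gloss, and that section 5.5.1 grants latitude rather than contradicting it. What remains is that the latitude has no criterion, and the tables cannot supply one.

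**Conclusion.** The point holds as an internal contradiction in current operative text, probably a drafting slip. The two wordings give different Table 5 rows for every child who first reacts at 10 mg or above, with starting doses 2 to 150 times apart, and the same row for first reactions at 0.5 or 3 mg. The unresolved handling of transient Grade 1 symptoms is a separate, smaller gap. In the worked case it changes the Phase 2 starting dose 12-fold and whether an escalation day applies.

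The effect is on consistency of starting dose, build-up time and supervision. No effect on the validity of the S versus C comparison, the sample size or the significance level is shown. The figures rest on Tables 2, 5 and 7 as printed, on tolerance of all doses below the first reaction, and on the minimum step length and target maintenance period. How often sites would read the sentence differently cannot be estimated from the documents.

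**What to change.** Reconcile the defining sentence in section 5.3.2.1 with its own gloss, with Table 5, with the stated Phase 1 duration and with section 5.5.1, so that one definition remains. State explicitly, for each phase, how transient Grade 1 symptoms count towards the NOAEL, and carry the same wording onto the CRF. Which definition and which handling of transient symptoms apply is for the sponsor's clinicians.

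The cost is about one corrected sentence in each of the two sections and a matching CRF entry. The sample size and analysis are unchanged.
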